STUDY PROTOCOL PLAN AND STATISTICAL ANALYSIS PLAN (SAP)

UNIVERSITY CEU CARDENAL HERRERA

Principal investigator: [name] [name]

TITLE: Ultrasound Probe Pressure on the Intratendon Doppler Signal in Patellar Tendinopathy

Research and Ethics Committee of CEU Cardenal Herrera University Number: CEI20/073

NCT ID:

DATE: 12-09-2020

STUDY PROTOCOL PLAN

Objectives:

The objectives of our study have been the following:

- Analyze the influence of the pressure exerted on the probe on the variables of area, number of signals, pixel intensity, perimeter, solidity, perfusion index, circularity, major and minor diameter of the intratendon Doppler signal in the evaluation of patellar tendinopathy.
- To study the relationship between the pressure exerted on the probe and intratendon perfusion in the Doppler evaluation of patellar tendinopathy.

Volunteers who want to participate in the study will read the general information of the study and sign the informed consent to participate in the study.

Once the informed consent has been read and delivered, the evaluator will check that they meet the inclusion criteria.

A quasi-experimental study of a single group will be carried out, consisting of subjects with patellar tendinopathy with intratendon hyper vascularization. Intratendon vascularization will be quantified using a proprietary methodology using ImageJ 1.47v image analysis software, determining the different variables related to the Doppler signal within an intratendon region of interest.

The first contact with the patient likely to participate in the project will always be made by the same researcher who will duly inform them of the study and provide informed consent in case of accepting participation for the performance of the exploratory ultrasound. Subsequently, a general questionnaire will be completed, where sociodemographic data and other data referring to the injury and sports practice are collected, also adding the VISA-P questionnaire that assesses the symptomatic severity, the severity of the symptoms and the capacity functional function in patients with patellar tendinopathy. Lastly, the ultrasound examination will be carried out in power-Doppler mode.

The ultrasound examination will begin with the positioning of the patient on the table in

the supine position and with both knees extended. At the level of the knee to be explored, a support with an articulated arm will be placed where the probe attached to the force meter will be fixed. After positioning the articulated arm, a power-Doppler ultrasound scan of the intratendon vascularization will be carried out, making longitudinal cuts of the patellar tendon and using previously pre-established Doppler optimization parameters for all patients. The optimization parameters of the power-Doppler signal will be set at a Doppler frequency of 6.7 MHz, pulse repetition frequency (PRF) of 0.7 kHz. The lowest wall filter and a standardized gain just below the level that produces random noise will be applied.

This examination will be repeated several times with different probe pressures, which will be quantitatively adjusted through the force sensor and maintained with the articulated arm. A 4-second static video will be recorded of the longitudinal section that presents a higher Doppler signal in each of the scans at different probe pressures.

These videos will be saved for later analysis with ImageJ 1.47v software (Wayne Rasband, National Institutes of Health, USA, 2012) to determine and quantify the presence of intratendon Doppler signal.

The processing and analysis of the videos and images will be carried out on the image with the highest and lowest Doppler signal of each stored video. Once the image has been scaled, a region of interest (ROI) with dimensions capable of encompassing the intratendon Doppler signal will be selected individually.

To quantify the Doppler signal, the saved image with the highest Doppler signal of each video was selected and the area of color pixels was calculated.

To quantify the flux, the pixel color mean of the Doppler signals of each image was calculated. The mean pixel color of the image with the highest signal was considered as data of the maximum systolic velocity, and the one with the lowest signal as the final diastolic velocity. These data were transferred to the IR formula, obtaining a value associated with the intratendinous flow pattern (perfusion index).

In the images that did not detect a Doppler signal, or did not present an intratendon Doppler signal in diastole, the IR was determined as 1, which represents normality in the musculoskeletal tissue.

In addition, the parameters of number of signals, mean intensity of the pixel, area,

perimeter, major and minor diameter, circularity and solidity were automatically calculated on the selected images with the highest Doppler signal of each recording.

This methodology will be carried out following the previously established and standardized order, based on standardized protocols for both subject positioning and echo-Doppler exploration. The ultrasound examination and subsequent analysis of the images will be described exactly and precisely so that they can be easily reproducible. All data obtained will be recorded in a computer spreadsheet to make the final statistical analysis easier and to obtain a greater and faster interpretation of the results.

Statistical Analysis Plan (SAP)

First, all the variables of interest will be detected and later they will be coded, labeled and transferred to a database. A data collection notebook (CDN) will be created where the variables, their reference values, measurement system and interpretation will be described and which will be available to all members of the working group. The programs used will be Microsoft © Access and Excel for initial data registration and IBM SPSS Statistics 19.0 for analysis.

Data debugging and control systems

The data related to the clinical information of the subjects and related to the questionnaires will be recorded in a database created for this purpose (Microsoft Access ©) with data entry protection systems. The same researcher will always record the data and a feedback review will be carried out for the detection of errors and lost cases by a third person. Missing and out-of-range screening will be performed.

The data related to the variables obtained by image analysis of ultrasounds will be exported in an automated way with a macro created for this purpose from the data analysis program in ASCII format to avoid incompatibilities between the image analysis program and the imaging programs. statistical analysis.

Exploratory Data Analysis (EDA)

Qualitative variables will be summarized in the form of counts and relative frequencies and, where appropriate, absolute frequencies and their confidence intervals (95% CI). Graphic summaries will be made using bar diagrams.

The quantitative variables will be summarized by means, standard deviations, medians, and interquartile ranges. Confidence intervals will also be provided for each of the measures. Graphical summaries will be made using box plots and bar diagrams with 95% CI.

A univariate analysis of outliers will be carried out and their influence will be verified through the Z scores. Multivariate analysis of atypical cases and their influence will be carried out using the Mahalanobis distance.

Unusual cases will be removed from the analysis only if it is certain that they are wrong.

It will be checked whether the quantitative variables of interest follow a normal distribution (Kolmogorov-Smirnov test). The normality tests will be accompanied by the Q-Q normality graphs with and without trend that will aid interpretation and decision-making. In the event that any of the variables of interest does not conform to a normal distribution, a transformation of this will be carried out until it is achieved as long as its interpretation is not compromised.

Analysis of data

In the case of fulfilling the assumption of normality, parametric tests will be chosen and if not, the non-parametric alternatives will be chosen.

The measurement pattern used will be randomized, all subjects will be assigned to a minimum or a maximum probe pressure as the start of the measurements. The randomization factor (pressure) is included as a fixed effect, which will prevent a possible

interaction between pressure and the quantification of the Doppler signal.

To perform the statistical analysis, in the case that the variables present normality, the Pearson correlation coefficient will be used for quantitative variables. In order to better visualize the joint behaviour of both variables, scatter diagrams will be added and to determine the effect size and interpret the degree of shared variance, the coefficient of determination will be calculated. In the event that any variable does not present normality, the Spearman Rho correlation test will be chosen.

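### The plan states no masking of the image reader to probe pressure, although frame, ROI and no-signal decisions come before any automatic measurement

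*Combined protocol and SAP*

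**What the plan says.** The relevant text is in the image-acquisition and image-processing paragraphs of the Study Protocol Plan.

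- **Acquisition.** Pressure is set through the force sensor and held by the articulated arm. The recording rule, applied at every pressure setting, reads: "A 4-second static video will be recorded of the longitudinal section that presents a higher Doppler signal in each of the scans at different probe" (cut before its last word).
- **Frame.** Processing "will be carried out on the image with the highest and lowest Doppler signal of each stored video". For signal area, "the saved image with the highest Doppler signal of each video was selected and the area of color pixels was calculated".
- **ROI.** After scaling, "a region of interest (ROI) with dimensions capable of encompassing the intratendon Doppler signal will be selected individually".
- **Perfusion index.** "The mean pixel color of the image with the highest signal was considered as data of the maximum systolic velocity", and the lowest-signal frame supplies the diastolic value. Where an image showed no signal, or "did not present an intratendon Doppler signal in diastole, the IR was determined as 1".
- **Other measures.** Number of signals, intensity, area, perimeter, diameters, circularity and solidity are computed automatically, on the frame already selected.

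Under Data debugging and control systems, the SAP adds that image variables are exported by "a macro created for this purpose". Under Analysis of data it randomises whether measurement starts at the lowest or the highest pressure. Neither document mentions masking of the image analyst, coded or shuffled files, a second reader of the images, or a reader-agreement check.

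**The concern.** The study has one group and one exposure, probe pressure, and both objectives concern how the Doppler measures relate to it. Every outcome passes through human selection before software measures anything. If the person selecting knows the pressure of each clip, any expectation about its effect can enter those selections.

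Such an error would be systematic with respect to the exposure. The correlation analysis in the SAP would count it as part of the pressure effect, and more patients would make the estimate more precise without removing the bias.

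**Working it through.** The documents give no figure to reproduce here, so the check sets each reading decision beside the outcomes it feeds, and then beside the safeguards that the plan does contain.

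**Step 1. Where judgement enters, and what depends on it**

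| Decision | Rule given | Outcomes affected |
|---|---|---|
| Highest-signal frame | Criterion stated; no method for finding the frame | All the Doppler outcomes |
| Lowest-signal frame | Same | Perfusion index |
| ROI | Large enough to contain the signal; no anatomical border rule | Whatever counts as intratendon: area, number of signals, and measures derived from them |
| Signal absent, or absent in diastole | No threshold | Perfusion index, set to 1 |

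**Step 2. Whether an existing safeguard covers these decisions**

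| Safeguard | What it covers | Hides pressure from the reader? |
|---|---|---|
| Automatic calculation of measures | Steps after frame selection | No |
| Macro | Export of results | No |
| Error review by a third person | Described for clinical and questionnaire data | No |
| Randomised starting pressure | Order of acquisition | No |
| Promise of an exact, reproducible description of image analysis | Reproducibility | No; it names no masking |

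**Step 3. What follows for the estimate**

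For patient *i* at pressure *p*, write the recorded value as

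Y(i,p) = T(i,p) + B(i,p) + E(i,p),

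where T is the value that an ideal reading would give, B the shift due to the reader's expectation, and E random error. If B has the same mean at every pressure, it moves the level of Y but not its mean trend with pressure. If the mean of B changes with pressure, then

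trend in mean Y = trend in mean T + trend in mean B.

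A Pearson or Spearman coefficient computed from Y alone cannot split the two terms. Masked reading in random order works on B: a reader who cannot tell the pressure cannot vary the expectation with it.

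**Step 4. Whether the size can be worked out**

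A size would need the reader shift, the within-patient and between-patient spread, the number of pressures and the number of patients. The documents give none of these. Any false-positive rate would merely restate the values assumed, so none is given here.

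**The case against.** The strongest reply has five parts.

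1. **Silence is not evidence of unmasked reading.** A reader might infer that the analyst knows the pressure and picks frames by eye. The documents say neither. They give a frame criterion and leave open how it is applied. This stands: the fault is an unstated safeguard.
2. **Individual selection of the ROI may mean per patient.** Per image is the more natural reading, but the text allows both. This stands, but the per-patient reading supplies neither masking nor a border rule.
3. **An ROI that contains all the signal leaves area unchanged.** This is right for signal well inside the tendon. It does not settle whether signal at the tendon edge counts as intratendon, which frame is used, or when signal is declared absent. The share of signal lying at the edge is unknown.
4. **The damage can be undone.** A reader might infer that reading bias could never be separated from a true effect. That goes too far: the videos are saved, so they can be coded, shuffled and read again.
5. **No direction is stated.** The documents contain no hypothesis that more pressure gives less signal, and for solidity or circularity a reader may have no direction to favour. This limits how uniform any bias would be across outcomes. It does not remove the opening for bias.

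The automatic calculation and the frame criterion, which is objective in principle, are real strengths. They narrow the room for judgement without closing it.

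**Conclusion.** The point holds as a gap in the plan, correctable at low cost. Frame, ROI and absence decisions come before every automatic measurement, and nothing in either document masks the person making them to the exposure. Those decisions could vary with pressure and bias the pressure-signal relationship.

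The conclusion rests on two assumptions: that no unstated masking procedure is in place, and that some judgement is needed to apply the frame, border and absence criteria. If masking is already intended, one sentence in the protocol settles most of the matter.

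It would be tempting to conclude that the pressure effect will be spurious or inflated. The documents do not support that: they show that bias is possible, not that it occurs, and they do not allow its size to be estimated.

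**What to change.** **Main change.** State in the protocol that stored clips receive random codes, are read in random order across patients and pressures, and are linked to the pressure key only after the image data have been exported. If clips have already been read, the same procedure can be applied as a re-read of the archive.

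**ROI.** Define it by the same anatomical tendon-border rule at every pressure, so that the border does not follow the colour on each image. A rule based on the tendon border is preferable to a box of fixed size, because a tendon that flattens under pressure could leave a fixed box taking in tissue outside it.

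**Frames, where feasible.** Choose the highest- and lowest-signal frames by coloured-pixel count within that ROI. The ROI must then be set before the frame, which reverses the order now described.

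**Cost.** File coding needs no extra patients, visits or readers. Automatic frame choice is new programming, since the planned macro is described for export only.

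**What remains.** Visible tendon compression may reveal the pressure in part. Masked reading also does nothing about acquisition, where the section with more signal is chosen at a pressure set during the scan; the report should acknowledge that limitation separately.

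### The perfusion index is built from power-Doppler pixel colour labelled as velocity and given a normal value of 1, with no velocity measurement, calibration or validation behind either step

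*Combined protocol and SAP*

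**What the plan says.** The Study protocol plan names a single imaging mode: "Lastly, the ultrasound examination will be carried out in power-Doppler mode". The settings given belong to that mode: "The optimization parameters of the power-Doppler signal will be set at a Doppler frequency of 6.7 MHz, pulse repetition frequency (PRF) of 0.7 kHz", with the lowest wall filter and "a standardized gain just below the level that produces random noise".

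The paragraph on flux then derives the perfusion index in four steps:

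- The raw measure is mean colour: "To quantify the flux, the pixel color mean of the Doppler signals of each image was calculated".
- The highest-signal frame supplies the systolic term: "The mean pixel color of the image with the highest signal was considered as data of the maximum systolic velocity".
- The lowest-signal frame supplies the diastolic term: "and the one with the lowest signal as the final diastolic velocity".
- The two are combined: "These data were transferred to the IR formula, obtaining a value associated with the intratendinous flow pattern (perfusion index".

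For images with no Doppler signal, or none in diastole, the next paragraph says that "the IR was determined as 1, which represents normality in the musculoskeletal tissue".

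The abbreviation IR is not expanded and the formula is not printed. The perfusion index appears by name in the first objective, among nine variables.

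**The concern.** The plan gives the index two properties that the measurement does not have. The first is that its inputs are velocities. In power Doppler the colour scale represents the power of the Doppler-shifted echo, not its frequency shift, so a brighter pixel does not mean faster blood. The second is that a value of 1 marks normal tissue. The documents do not establish that reference for a ratio of pixel intensities.

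What is at stake is the conclusion that may be drawn. If the index changes with probe pressure, a reader of the plan would take this as a change in systolic and diastolic flow velocity, or as movement towards or away from normal. Neither reading follows from the recordings. The coding rule adds to the difficulty: a pressure that abolishes the signal produces a normal value by assignment, not by measurement.

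**Working it through.** The documents state no figure for this index, so there is nothing to reproduce. The check is a comparison of passages, followed by an illustration with assumed values.

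**1. What is recorded against what is claimed.** The Study protocol plan specifies power Doppler, its frequency, its pulse repetition frequency, a wall filter and a gain rule. It mentions no spectral trace, sample gate, angle correction or colour-velocity map. It mentions no conversion of pixel value to velocity and no comparison with a velocity-based index. The SAP adds none of these. The flux paragraph nonetheless names its two inputs as velocities.

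**2. Does forming a ratio recover velocity?** The formula is not printed, so I assume the usual form

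index = (S − D) / S,

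with S and D the values from the highest- and lowest-signal frames.

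- If S and D were velocities of 10 and 3 (assumed), the index would be (10 − 3)/10 = 0.70.
- Suppose instead that the pixel shows log-compressed power: pixel = 255 × (1 + 10·log10(P/Pmax)/R), with display range R in dB and the highest frame at Pmax. The index then reduces to −10·log10(power ratio D/S)/R, and velocity does not enter. For example, with a power ratio of 0.5 and R = 20, it is 3.01/20 = 0.151.

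| Power ratio D/S | R = 20 dB | R = 30 dB | R = 40 dB |
|---|---|---|---|
| 1.0 | 0.000 | 0.000 | 0.000 |
| 0.8 | 0.048 | 0.032 | 0.024 |
| 0.5 | 0.151 | 0.100 | 0.075 |
| 0.2 | 0.349 | 0.233 | 0.175 |

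Under these assumptions, two frames with equal echo power give an index of 0 even if the underlying velocities would give 0.70.

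**3. Sensitivity to the colour scale.** Assumed pixel values of 200 and 100 give (200 − 100)/200 = 0.50. Adding 50 to both gives 100/250 = 0.40, and adding 100 gives 100/300 = 0.33. A ratio of true velocities does not depend on the display in this way.

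**4. The two cases coded as 1.** In the assumed form:

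- Signal in the highest frame and none in the lowest, with absent signal entered as zero: (S − 0)/S = 1. The value follows from arithmetic.
- No signal in either frame: (0 − 0)/0, which is undefined. Here the value 1 is imposed.

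The plan gives both cases the same value and the same meaning.

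The tabulated values and the shifts show what can happen. They do not estimate what happens in this trial, because the documents do not give the colour map or display range.

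**The case against.** The best defence is that the plan's wording is softer than a claim to have measured velocity. Pixel colour is only considered as velocity data, the result is only associated with a flow pattern, and the method is described as proprietary. Read that way, the index is an empirical summary of how much the signal varies within a 4-second video. This part stands, and it is why the index can be kept. It does not cover the naming of the inputs as velocities or the statement about normality.

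Several stronger readings are tempting, and the documents do not support them:

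- *The trial will report a change in vascular resistance.* The word resistance does not appear. A resistance-type index is the natural reading of IR with systolic and diastolic inputs, but it is inferred.
- *The second objective fails because it rests on this index.* That objective refers to intratendon perfusion and does not say that this index measures it. The similarity of name suggests a link but does not establish one.
- *Probe pressure distorts the index through depth and attenuation.* The documents give no data on this. Both frames come from one video at one held pressure, so on a linear scale a common factor k cancels: (kS − kD)/(kS) = (S − D)/S. It would fail to cancel only on a non-linear or offset scale, and the scale is not given. Cancellation would answer the attenuation argument, but the remaining ratio would still be one of signal power.
- *Perfusion conclusions should move to coloured-pixel area, with this index demoted to descriptive.* Area also depends on gain and attenuation, so this would be a preference and not a correction.

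It can also be said that the meaning of the power-Doppler scale is not in the documents. It is what defines the mode, and the plan names the mode.

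**Conclusion.** The point holds for the meaning attached to one variable. The perfusion index cannot support a conclusion about flow velocity, and its value of 1 cannot be read as velocity-based normality, because the documents describe only power-Doppler acquisition and no calibration or validation. The labelling applies to every index value at every pressure. How far the index departs from a velocity-based one cannot be derived.

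The conclusion rests on the general property that power Doppler displays signal power. The comments on the arithmetic of the index, including the two cases coded as 1, rest in addition on the assumed form (S − D)/S. The link to the second objective and any effect of pressure through attenuation remain assumptions, and the conclusion does not need them. The other eight variables in the first objective do not use the velocity reading. The change should be made, but it concerns labelling and permitted conclusions and does not undermine the trial as a whole.

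**What to change.** In the Study protocol plan, in the paragraphs on flux and on images without signal:

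1. Delete the equation of pixel colour with systolic and diastolic velocity, and the statement that 1 represents normality.
2. Define the index as the relative variation in mean power-Doppler pixel intensity between the highest- and lowest-signal frames, print its formula, and limit conclusions to that quantity.
3. State that a video with signal in the highest frame and none in the lowest has index 1 by arithmetic, if the formula is (S − D)/S with absent signal entered as zero.
4. State that a video with no signal at all has an undefined index, and that such videos are counted and reported separately at each pressure, not entered as normal.

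No new recordings are needed. The cost is that the trial gives up any claim about flow velocity or normality from this index, and that there are fewer index values at pressures that abolish the signal. The second objective and the other variables can stay as they are on this ground.

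### Scans with no Doppler signal are given a perfusion index of 1 and enter the pressure correlation unflagged, so loss of signal can pass for a change in perfusion index

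*Combined protocol and SAP*

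**What the plan says.** The second objective is "To study the relationship between the pressure exerted on the probe and intratendon perfusion", and the perfusion index is also among the variables listed in the first. Participants are "subjects with patellar tendinopathy with intratendon hyper vascularization", so each enters with a signal. The scan protocol states: "This examination will be repeated several times with different probe pressures". The number and levels of the pressures are not given.

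The image-processing text takes the mean pixel colour of the highest-signal image as systolic velocity and that of the lowest-signal image as diastolic velocity, and enters both in an IR formula that is not shown. For absent signal the rule is: "images that did not detect a Doppler signal, or did not present an intratendon Doppler signal in diastole, the IR was determined as 1". The reason offered is that "the IR was determined as 1, which represents normality in the musculoskeletal tissue".

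Other variables, including "the parameters of number of signals, mean intensity of the pixel, area", "were automatically calculated on the selected images with the highest Doppler signal of each recording".

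On data checks, the SAP says "Missing and out-of-range screening will be performed" (Data debugging and control systems). Exploratory Data Analysis adds Z-score and Mahalanobis checks, with removal only of values known to be wrong. Analysis of data plans Pearson correlation with scatter diagrams, or Spearman if normality fails. It does not name the pressure–IR pair. That pair follows from the objectives.

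**The concern.** Two states share one number. In the first, systolic signal is present and diastolic signal is not. In the second, nothing is detected and there is no flow pattern to index. Calling the second state normal is hard to defend in tendons selected for hypervascularization, when the question is what the probe does to the signal.

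Under the assumed formula, 1 is also the largest value IR can take. If blanks become more common as pressure rises, the correlation is pushed upward. If they become less common, it is pushed downward. If they are unrelated to pressure, they create no trend but weaken a real one.

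Loss of signal under pressure is a legitimate finding and should be shown as such. As planned, it would be merged into the IR correlation, and a reader could not tell how much of the coefficient came from scans in which no IR was measured.

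**Working it through.** **No figure to reproduce.** The documents give no sample size, number of pressures, effect size, SD or rate of signal loss. Every simulation input below is an assumption.

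**Algebra.** Let S be the systolic value, D the diastolic value, and assume IR = (S − D)/S.
- S > 0, D = 0: IR = S/S = 1, a computed value.
- S = 0, D = 0: IR = 0/0, undefined. The 1 is imputed.

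**Would the plan catch it?**
- Missing and out-of-range screening: an assigned 1 is neither missing nor out of range. This check also sits in the paragraph on clinical and questionnaire data. Image variables are described separately as a macro export.
- Outlier rule: a value set by protocol is not known to be wrong, so it stays.
- Scatter diagrams: they would show a cluster at 1, but not which state produced it.
- Spearman: the assigned values tie at the top rank, so ranking does not remove the effect.
- Area and number of signals come from the highest-signal image of each recording. If blanks are recorded as 0, these variables identify them, but no such use is planned.

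**Model A: every loss is a total blank, unrelated to IR.** IR = 0.6 + subject effect (SD 0.1) + error (SD 0.1), capped at 0.99; 20 subjects, 5 equally spaced pressures; lost scans set to 1; 2000 replicates. Spearman is used because a point mass at 1 cannot be transformed to normality. Entries are mean rho.

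| Loss pattern | True IR flat (rho 0) | True IR fall of 0.10 (rho −0.24) |
|---|---|---|
| Rising 0 to 10% | +0.06 | −0.16 |
| Rising 0 to 20% | +0.12 | −0.07 |
| Rising 0 to 40% | +0.25 | +0.09 |
| Rising 0 to 60% | +0.37 | +0.26 |
| Constant 20% | 0.00 | −0.15 |
| Constant 40% | 0.00 | −0.09 |

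With flat IR and loss falling to 0 from 20% or 40%, rho is −0.12 or −0.25. Over 10–40 subjects and 3–8 pressures, the four rising-loss figures for flat IR range over +0.05 to +0.07, +0.11 to +0.14, +0.23 to +0.28 and +0.34 to +0.44.

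A separate run with independent scans (SD 0.15, mean IR 0.5 or 0.7) gave the same Spearman values. Pearson at 20 subjects gave +0.07 to +0.10, +0.13 to +0.17, +0.24 to +0.30 and +0.35 to +0.41. So the effect does not depend on which coefficient is chosen.

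**Model B: a detection floor, so loss depends on IR.** S is lognormal (subject SD 0.4, scan SD 0.2) and falls 60% across the pressures; D = S(1 − IR); anything below the floor is undetected. The floor is a fraction of the median systolic signal at the lowest pressure; 1000 replicates. True rho means rho of IR without a detection limit.

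| Floor | Flat IR: present rule | Blanks removed | Both signals present | Fall of 0.10: present rule | Blanks removed | Both signals present |
|---|---|---|---|---|---|---|
| 0.1 | +0.06 | +0.06 | −0.08 | −0.20 | −0.20 | −0.28 |
| 0.2 | +0.27 | +0.25 | −0.15 | +0.05 | +0.03 | −0.34 |
| 0.3 | +0.35 | +0.30 | −0.17 | +0.23 | +0.15 | −0.34 |

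At floor 0.2 with flat IR, blanks rise from 0 to 6% across the pressures, and diastole-only loss from 15% to 62%. Diastole-only loss therefore drives most of the movement there, and restricting to scans with both signals errs the other way. Across 162 settings with a 60% or 80% signal fall, the true rho always lay between the present-rule and both-signals results.

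**The case against.** The strongest reply has three parts.

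**The rule may be a coherent score.** If compression removes first diastolic and then systolic signal, placing both at the no-flow end is a defensible ordinal scale, and a positive correlation is then a result. The rule is also prespecified with a reason. This stands as a possible reading, but the plan does not say that IR is to be read this way. Even on this reading, the reader needs to know how many values were assigned.

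**Total blanks may be rare and may matter little.** The tendons are hypervascular, gain is set just below noise, and the best image of each video is used. In Model B, removing blanks alone usually moves rho by only a few hundredths. This stands. Model A's larger figures need every loss to be a total blank. For this reason, deleting blanks is not offered as the remedy.

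**Some figures are conditional.** The ceiling at 1 rests on the assumed formula. The bracketing result holds only in the settings tested. With no fall in signal and a floor of 0.3, a true rho of about +0.24 comes out near +0.20 under both codings. This also stands.

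The existing checks earn partial credit. Objective 1 covers area and number of signals, so signal loss would not be wholly invisible. Nothing, however, links it to the IR result.

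**Conclusion.** The concern holds. The plan assigns a value to scans in which no IR was measured, places it at the top of the scale under the assumed formula, and provides no flag, count by pressure or sensitivity analysis. If loss depends on pressure, the result for Objective 2 can change size or sign. In Model A, a true rho of −0.24 becomes +0.09 when loss reaches 40% at the highest pressure. If loss is unrelated to pressure, a real correlation is only weakened.

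Confidence is high that the safeguard is missing. The size of any distortion is unknown, because it depends on a loss rate that the documents do not give. This should be fixed before analysis.

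**What to change.** 1. Write out the IR formula. Where no signal is detected, code IR as undefined with a flag, and record area and number of signals as 0. Put the rule in the data collection notebook that the SAP already promises.
2. Report by pressure the share of scans with no signal and, separately, with no diastolic signal. Analyse the trend allowing for repeated scans per subject, for example by GEE logistic regression with subject as cluster. Give counts only if losses are very few. Read the IR results beside this table.
3. Analyse IR among scans with systolic signal, stated as conditional on detection. Show the present coding and the both-signals subset as sensitivity analyses. State that a diastole-only IR of 1 can reflect the detection limit, and that the both-signals subset can be biased the other way if scans with high IR lose diastolic signal first. Present none of the three as unbiased.

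**Cost.** SAP wording, one table, one trend model and two sensitivity runs on stored videos. Precision falls at pressures with much loss. In Model A, 40% loss leaves 20 × (1 − 0.40) = 12 scans at the highest pressure, so the interval for that mean is √(20/12) = 1.29 times as wide. Power for a true fall of 0.10 drops from about 74% to 58% (ordinary Spearman test on pooled scans, two-sided 5%). The change makes the problem visible but does not remove it.
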